EudraCT	European Clinical Trials Database
EudraVIGILANCE	European database for Pharmacovigilance
GCP	Good Clinical Practice
GMP	Good Manufacturing Practice
IB	Investigator's Brochure
ICF	Informed Consent Form
ICH	International Conference on Harmonisation of technical requirements for registration of pharmaceuticals for human use.
IMP	Investigational Medicinal Product
IMPD	Investigational Medicinal Product Dossier
ISF	Investigator Site File (This forms part of the TMF)
ISRCTN	International Standard Randomised Controlled Trials Number
LCTU	Leicester Clinical Trials Unit
МА	Marketing Authorisation
MHRA	Medicines and Healthcare products Regulatory Agency
MS	Member State
NHS R&D	National Health Service Research & Development
NIMP	Non-Investigational Medicinal Product

Page **6** of **60**

PI	Principal Investigator
PIC	Participant Identification Centre
PIS	Participant Information Sheet
QA	Quality Assurance
QC	Quality Control
QP	Qualified Person
RCT	Randomised Control Trial
REC	Research Ethics Committee
SAE	Serious Adverse Event
SAR	Serious Adverse Reaction
SDV	Source Data Verification
SOP	Standard Operating Procedure
SmPC	Summary of Product Characteristics
SSI	Site Specific Information
SUSAR	Suspected Unexpected Serious Adverse Reaction
TMF	Trial Master File
TMG	Trial Management Group
TSC	Trial Steering Committee
VOC	Volatile Organic Compound
WOCBP	Woman of Child Bearing Potential

Page **7** of **60**

iii. TRIAL SUMMARY

This will be a single-centre, double-blinded, placebo- controlled, parallel group, randomised controlled trial comparing MSTT1041A (anti-ST2 antibody) versus placebo in COPD. MSTT1041A 490mg subcutaneous (s/c) or matched placebo dosed every 4 weeks for a total of 12 doses. Patients will be followed up for 60 weeks (i.e. 48 week treatment period and 12 week follow-up), with secondary outcome measures at baseline, 4, 12, 24, 36, 48 and 60 weeks and at exacerbations events presenting prior to treatment initiation. (Trial schedule and assessments are detailed in Appendix 1). The dose and dosing interval has been derived from an earlier PK/PD modelling and is the highest dose included in an ongoing phase 2b asthma study. The primary outcome measure is exacerbation frequency. Exacerbation events are relatively infrequent and can be affected by season, therefore we have chosen a 48 week treatment duration with follow-up out to 12 months.

Trial Title	A randomised placebo-controlled trial of anti-ST2 in COPD									
Short Title	Anti-ST2 in COPD									
Trial Acronym	COPD-ST ₂ OP									
Clinical Phase	lla									
Trial Design	Single-centre, double-blinded, placebo-controlled, parallel group, randomised controlled trial									
Trial Participants	Moderate to very severe COPD (GOLD II to IV)									
Planned Sample Size	80									
Treatment duration	48 weeks									
Follow up duration	12 weeks									
Planned Trial Period	60 weeks (+/- 2 weeks)									
Planned Recruitment Period	Up to 9 months									
Investigational Medicinal Product(s)	Anti-ST2									
Formulation, Dose, Route of Administration	Injectable, 490mg, subcutaneous									
Primary Objective	To evaluate the efficacy of anti-ST2 versus placebo on frequency of moderate-to-severe exacerbations (health care utilisation resulting in treatment with systemic corticosteroids and/or antibiotics) in 48 weeks as add-on to standard of care									
Primary Outcome Measures	 Annual/48 week COPD exacerbation frequency where an exacerbation is defined by symptomatic worsening of COPD requiring: use of systemic corticosteroids for at least 3 days; a single depot injectable dose of corticosteroids will be considered equivalent to a 3-day course of systemic corticosteroids; and/or use of antibiotics; and/or an inpatient hospitalisation or death due to COPD 									
Secondary Objectives	Safety and tolerability, patient related outcomes (PROs), lung function and inflammatory cell differentials in sputum and blood.									
Exploratory Objectives	Systemic inflammation, upper airway inflammation, airway infection and ecology, breath volatile organic compound profiling, quantitative airway geometry and densitometry, mediators, cell subset analysis and pharmacogenomics.									
Subgroup Objectives	Rate of protocol defined COPD exacerbation through 48 week treatment period, SGRQ-c and FEV1 in subgroups defined by baseline blood eosinophil count.									

iv. FUNDING AND SUPPORT IN KIND

FUNDER(S)	FINANCIAL AND NON-FINANCIAL SUPPORT GIVEN
Genentech South San Francisco California USA	Financial support and provision of the drug and placebo
NIHR Biomedical Research Centre (BRC) and Clinical Research Facility (CRF)	Local infrastructure support

v. ROLE OF TRIAL SPONSOR AND FUNDER

The trial sponsor, University of Leicester, will be responsible for all aspects of the trial as per ICH-GCP, apart from where these duties have been delegated to the Leicester Clinical Trials Unit. The funder, Genentech, will be responsible for funding the trial, supplying the drug and placebo, performing certain sample analysis not available at Leicester. Data and samples will be shared between the Sponsor and Funder and the Funder will be provided with all Protocols and SOPs for their comment and input.

vi. ROLES AND RESPONSIBILITIES OF TRIAL MANAGEMENT COMMITEES/GROUPS & INDIVIDUALS

Trial Management Committees

The TMG will comprise of the trial Chief Investigator, Trial Clinical Co-ordinators, Trial Manager, Database Developer (as required), Trial Statistician and a Research Nurse. The TMG will be responsible for the day-to-day management of the trial. The TMG is responsible for all aspects of the trial (including recruitment rate, budget management, safety reporting, protocol compliance etc.) and for ensuring appropriate action is taken to safeguard trial participants and the quality of the trial.

Trial Steering Committee (TSC)

The TSC will comprise of an Independent Chairperson, Chief Investigator, Funder Representative and other Independent Members including Patient Representative. The TSC will provide oversight of the trial and monitor the progress of the trial to ensure it is being conducted in accordance with the protocol, relevant regulations and the principles of GCP.

Data Safety Management Committee (DSMC)

The DSMC will consist of independent experts who will assess the progress, conduct, participant safety and critical endpoints of a clinical trial. The DSMC will adopt a DAMOCLES charter to define its terms of reference and operation and will make recommendations to the TSC. The DSMC will meet on a regular basis as specified in the DSMC charter to review the

Page 9 of 60

trial information and accruing data during the conduct of the trial and make recommendations to the TSC.

vii. Protocol contributors

- [name] and [name], Respiratory BRC- trial design and protocol write up.
- [name], [name] and [name], Leicester Clinical Trials Unit sample size, statistical analysis & randomisation.
- [name] and [name], Leicester Clinical Trials Unit trial management, safety reporting & pharmacovigilance, randomisation, data management, quality assurance.

viii. KEY WORDS: anti-ST2, moderate to very severe COPD, safety and efficacy, randomised trial

ix.TRIAL FLOW CHART

(See Appendix 3)

Fig 1: Schematic of Trial Design for anti-ST2

Study start	Randomisation		Scheduled 4-weekly dosing, assessment at 0, 4, 12, 24, 36, 48 weeks. Follow up period 60 weeks. Unscheduled exacerbations. intervention									on p	Follow up period and end of study	
	Anti-ST2													
													·	
	Placebo												$ \rightarrow $	
													r	
eks -2 ent & ning	0 Dosing & assessment	4 Dosing & assessment	8 Dosing	12 Dosing & assessment	16 Dosing	20 Dosing	24 Dosing & assessment	28 Dosing	32 Dosing	36 Dosing & assessment	40 Dosing	44 Dosing	48 Assessmen	6 t Assess

Page 10 of 60

1 BACKGROUND and rationale for conducting this trial

Chronic obstructive pulmonary disease (COPD) is a significant cause of morbidity and mortality worldwide[1]. In contrast to other chronic diseases, COPD is increasing in prevalence and is projected to be the third-leading cause of death and disability worldwide by 2030[2]. The costs to society for treating COPD are high, accounting for approximately 3.4% of the total health care budget of the European Union.

Acute exacerbations of COPD (AECOPD) are responsible for a large portion of the economic burden of COPD. More than 500,000 hospitalisations and 100,000 deaths are attributed to AECOPD in the US each year [3]. In addition to a substantial economic burden, AECOPD is also responsible for much of the morbidity and mortality from COPD.

Interleukin-33 (IL-33) is an alarmin released from the epithelium following damage [4]. IL-33 is an IL-1 family alarmin cytokine constitutively expressed at epithelial barrier surfaces where it is rapidly released from cells during tissue injury. IL-33 signals through a receptor complex of IL-1 receptor-like 1 (IL1RL1) (known as ST2) and IL-1 receptor accessory protein (IL1RAcP) to initiate MyD88-dependent inflammatory pathways[5]. The role of the IL33/ST2 axis in COPD is uncertain. IL33 has been implicated in eosinophil recruitment to the airway and maturation in the bone marrow largely via its effects upon innate lymphoid cells[6]. IL33 increased following experimental cold in asthma and thus might play a role in the consequent inflammatory response and possible susceptibility to secondary bacterial infection in obstructive lung disease [7]. Both eosinophilic inflammation and viral infection drive COPD exacerbations and therefore targeting the IL33/ST2 axis might reduce COPD exacerbations.

2 Assessment and management of risk

Beyond standard of care the participants will undergo additional blood tests, breathing tests, airway sampling, and a non-contrast CT scan and a SC IMP. These are all common routine tests. The blood, breath and airway sampling has minimal risk and mild discomfort. The non-contrast CT scan will involve radiation but the increased risk of cancer from radiation in an elderly population with a significant smoking history will have a high lifetime risk and therefore the radiation exposure will present a very small increase in this risk. The IMP both placebo and drug can potentially cause local reactions. Anti-ST2 has been tested in healthy volunteers and a phase 2b trial in asthma is currently ongoing. The target is anticipated to reduce exacerbation risk and symptoms and therefore might reduce risk in those individuals. Based on the three completed Phase I clinical trials and the ongoing Phase IIb trial in patients with uncontrolled severe asthma, the safety profile for anti-ST2 remains favourable at this time. We will also monitor and analyse all potential cases of anaphylaxis and major adverse cardiac events (MACE).

• Risk Type C = Markedly higher than the risk of standard medical care

3 OBJECTIVES AND OUTCOME MEASURES

3.1 **Primary objective**

We hypothesise that anti-ST2 will impact on airway inflammation in COPD and consequently will reduce COPD exacerbation frequency.

The primary objective of the trial is to evaluate the efficacy of anti-ST2 versus placebo on frequency of moderate-to-severe exacerbations (health care utilisation resulting in treatment with systemic corticosteroids and/or antibiotics or hospitalisation or death due to COPD, respectively) in 48 weeks as add-on to standard of care.

3.2 Secondary Objectives

Another key objective is to assess the safety and tolerability of SC doses of anti-ST2 compared to placebo in adult patients with moderate to very severe COPD.

Additionally, to assess the effects of anti-ST2 versus placebo both during stable visits and at the exacerbation events on the following:

- 1. Symptoms
- 2. Health status
- 3. Lung function
- 4. Inflammatory cell differentials
 - i. Sputum cell count
 - ii. Blood cell count
- 5. Airway morphometry
- 6. Pharmacogenomics

3.3 Exploratory Objectives

- 1. Systemic inflammation
- 2. Upper airway inflammation
- 3. Airway infection and ecology
- 4. Breath volatile organic compound profiling
- 5. Quantitative airway geometry and densitometry
- 6. Pharmacogenomics
- 7. Pharmacokinetics and ADA level
- 8. Pharmacogenomics response analysis in subgroups determined by SNPs for alleles associated with the IL33/ST2 axis.

3.4 Subgroup Objectives

• To evaluate the efficacy of anti-ST2 versus placebo on the outcome rate of protocoldefined COPD exacerbations through 48 weeks treatment period, patient reported outcomes (PROs) [SGRQ-c], and lung function [FEV1] in subgroups defined by baseline blood eosinophil count.

3.5 Outcome measures

3.5.1 Primary outcome

The primary outcome is: Frequency of moderate to severe exacerbation (defined as requiring treatment with systemic corticosteroids and/or antibiotics in the community or hospital or hospitalisation) in 48 weeks.

*where a COPD exacerbation is defined by symptomatic worsening of COPD requiring:

 Use of systemic corticosteroids for at least 3 days; a single depot injectable dose of corticosteroids will be considered equivalent to a 3-day course of systemic corticosteroids;

and/or

Use of antibiotics;

and/or

> An inpatient hospitalisation or death due to COPD

For a detailed layout of the timeline for all visit procedures please refer to Appendix 1 Schedule of Procedures.

3.5.2 Secondary outcomes (**indicates this data is held on Macro database*)

1. Safety and tolerability

- AE event rate in the 48 weeks of the trial from first dose*
- SAE event rate in the 48 weeks of the trial from first dose*

2. Patient related outcomes (PROs) (weeks 0, 4, 12, 24, 36 and 48)*

- St George's Respiratory Questionnaire for COPD patients (SGRQ-c)
 Total
- COPD Assessment Test (CAT)
- mMRC Dyspnoea Scale
- Visual analogue score (VAS)
 - Dyspnoea
 - Cough
 - Sputum production
- Sputum purulence colour card

3. Lung function (Weeks 0 and 48)

- Pre and post BD spirometry*
 - FEV1
 - FEV1 % predicted
 - FVC
 - FEV1/FVC %
 - BD reversibility %
- Whole body plethysmography (body box)*
 - TLC
 - RV
 - RV/TLC %

4. Inflammation (Weeks 0, 4, 12, 24, 36)

- Cell count
 - Blood inflammatory cell differentials*
 - o WBC
 - \circ Eosinophils
 - \circ Neutrophils
 - Sputum inflammatory cell differentials
 - Eosinophils
 - o Neutrophils
 - o Macrophages
 - \circ Lymphocytes
 - Epithelial cells
 - o Total

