4 TRIAL DESIGN

This is a single-centre, double-blind, placebo- controlled, parallel group, randomised controlled trial to assess the efficacy and safety of anti-ST2 compared to placebo, in patients with moderate to very severe COPD (GOLD II-IV). Anti-ST2 will be administered via subcutaneous injection once every 4 weeks (Week 0, 4, 8, 12, 16, 20, 24, 28, 32, 36, 40, and 44) during the 48-week treatment period. The treatment period will be followed by a 12-week follow-up period (i.e washout period). An overview of the trial design is presented in Figure 1.

After signing the informed consent at the initial visit, patients will enter a screening period within 7-14 days of randomisation. Patients who qualify to participate in the trial will be randomised into a 48-week treatment period in which they will receive either 490 mg anti-ST2 or a matching placebo. Patients will be evaluated for an additional 12 weeks following completion of the efficacy endpoint (visit 13, week 48). Treatment groups will remain blinded until the 60-week follow-up period is completed, and trial database is locked. Visit procedures will be performed as shown in Appendix 1.

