8.6 Dosage schedules

See figure 1 for dosing schedule. In animal trial and phase I human studies both, intravenous and subcutaneous (SC) routes were used, with no significant difference in safety. For ease of administration we will be using the SC route in this trial. The drug dose is fixed at 490mg every 4 weeks for 12 visits.

A window of up to 4 weeks will be allowed within which a participant will be able to delay or miss taking a scheduled dose. A delay will then be carried through to all their subsequent study visits. If the participant misses a dose it will be recorded in the notes and the next scheduled dose will be administered. Participants will be allowed to miss a single dose of the study drug (See Section 7.7) and are permitted up to a 4 week treatment delay.

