9.3 Recording and reporting of SAEs, AESIs, SARs AND SUSARs

All **SAEs** / **SUSARs** occurring from the **point of randomisation** until the final trial visit following follow-up (or 100 days post cessation of trial treatment (if discontinued early), must be recorded on the SAE Form and sent to the Sponsor and the Leicester Clinical Trials Unit (LCTU) **within 24 hours** of the research staff becoming aware of the event.

Page 28 of 60

After informed consent has been obtained but prior to initiation of study drug, only serious adverse events caused by a protocol-mandated intervention (e.g., invasive procedures such as biopsies, discontinuation of medications) should be reported.

Accidental overdoses or medication errors must report to the Sponsor within 24 hours after learning of the event, regardless of relationship to study drug.

Adverse events of special interest (AESIs) are required to be reported by the investigator to the Sponsor immediately (i.e., no more than 24 hours after learning of the event.

Once all resulting queries have been resolved, the Sponsor will send an acknowledgement of the closure of the SAE, all correspondence and signed SAE forms will be retained by the site, within the Trial Master File and electronically on the Sponsor SAE database.

For each **SAEs / SUSARs** the following information will be collected:

- full details in medical terms and case description
- event duration (start and end dates, if applicable)
- action taken
- outcome
- seriousness criteria
- causality (i.e. relatedness to trial drug / investigation), in the opinion of the investigator
- whether the event would be considered anticipated.

Any change of condition or other follow-up information should be faxed to the Sponsor as soon as it is available or at least within 24 hours of the information becoming available. Events will be followed up until the event has resolved or a final outcome has been reached.

All SAEs assigned by the CI or delegate (or following central review) as both suspected to be related to IMP-treatment and unexpected will be classified as SUSARs and will be subject to expedited reporting to the Medicines and Healthcare Products Regulatory Agency (MHRA). The sponsor will inform the MHRA and the REC of SUSARs within the required expedited reporting timescales. Fatal or life-threatening SUSARs must be reported within 7 days and all other SUSARs within 15 days.

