#### 1. Safety and tolerability (All visits)

- AE event rate in the 48 weeks of the trial from first dose\*
- SAE event rate in the 48 weeks of the trial from first dose\*

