# 7 Safety and Adverse Events

All safety data will be presented according to the safety population. Any adverse events and serious adverse events occurring from the first dose throughout the trial period will be recorded on the AE CRF, Sponsor's SAE form and SAE tracking log.

An Adverse Event (AE) is any untoward medical occurrence in a patient, associated with the use of a medicinal product, whether or not considered related to the medicinal product.

Events meeting the definition of an AE include:

- Exacerbation of a chronic condition (except COPD)
- New conditions detected or diagnosed after trial treatment administration even though it may have been present prior to the start of the trial
- Signs, symptoms, or the clinical sequelae of a suspected interaction
- Signs, symptoms, or the clinical sequelae of a suspected overdose of trial treatment
- Any unfavourable and unintended sign (including an abnormal laboratory finding), symptom, or disease temporally associated with the use of a medicinal product, whether or not considered related to the medicinal product
- Recurrence of an intermittent medical condition (e.g., headache) not present at baseline
- Any deterioration in a laboratory value or other clinical test (e.g., ECG, X ray) that is associated with symptoms or leads to a change in study treatment or concomitant treatment or discontinuation from study drug
- Adverse events that are related to a protocol mandated intervention, including those that occur prior to assignment of study treatment (e.g., screening invasive procedures such as biopsies)

Events that **do not** meet the definition of an AE include:

- Medical or surgical procedure (e.g., endoscopy, appendectomy); the condition that leads to the procedure is an AE
- Situations where an untoward medical occurrence did not occur (social admission to a hospital)
- COPD exacerbation, progression, signs and symptoms (unless they are considered to be related to the trial drug by the investigator; then they would constitute a reaction)

An adverse reaction (AR) is an untoward and unintended response(s) related to the study treatment. All cases judged by either the reporting medically qualified professional or the sponsor as having a reasonable suspected causal relationship to the study treatment qualify as adverse reactions.

A Serious Adverse Event (SAE) or Serious Adverse Reaction (SAR) is defined as any adverse event or adverse reaction in a trial participant that:

- Results in death

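### The AE and SAE rate outcomes stop 48 weeks after first dose, leaving 12 of the 16 scheduled weeks after the last dose outside the between-arm safety rate

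*Protocol*

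**What the plan says.** **Outcome window.** Protocol 3.5.2 lists two safety outcomes, AE rate and SAE rate. The second reads "SAE event rate in the 48 weeks of the trial from first dose". SAP 2.2.1 carries the same limit ("AE event rate in the 48 weeks of the trial from first dose"), but under the heading "Safety and tolerability (All visits", which takes in Visit 14 at week 60.

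**Dosing.** Protocol section 4 sets injections "once every 4 weeks (Week 0, 4, 8, 12, 16, 20, 24, 28, 32, 36, 40, and 44". Section 8.6 says participants "are permitted up to a 4 week treatment delay" and adds: "A delay will then be carried through to all their subsequent study visits".

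**Collection.** The schedules in Protocol Appendix 1 and SAP Table 1 mark AE/SAE assessment at every visit from Visit 1 to Visit 14. Protocol 9.3 requires SAE reporting from randomisation "until the final trial visit following follow-up (or 100 days post cessation of trial treatment (if discontinued early". Protocol 9.9 continues recording of drug reactions for up to 3 months after the last dose. SAP section 7 says that events "occurring from the first dose throughout the trial period will be recorded on the AE CRF".

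**Reporting.** SAP section 7 plans a listing of every adverse event, and SAP Appendix 2 gives a line listing with start date and arm. SAP Table 7 counts 'treatment-emergent' events without defining the term. SAP Table 8 gives total AEs and SAEs without that label. Neither table states a time window or a person-time denominator.

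**The concern.** Protocol 3.2 names safety and tolerability as a key objective, and Protocol 13.6.1 describes this as the first study of the antibody in COPD, with a human safety profile not yet fully known. Section 9.2.1 raises anti-drug antibodies, infection and possible cardiovascular risk, none of which need end when dosing ends. The amendment history records that the week-60 visit was put back after the regulator did not accept its removal on medical grounds. That shows the period was kept for a safety purpose.

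The only safety outcomes that the plan defines as rates nevertheless stop about one dosing interval after the last scheduled injection. Most of the follow-up after treatment then contributes neither events nor person-time to the between-arm comparison. Because the SAP heading and its bullets disagree, and Tables 7 and 8 state no window, two analysts working from the same plan could also produce different safety tables.

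**Working it through.** **Inputs.** Twelve doses at 4-week intervals; a 48-week treatment period plus a 12-week follow-up; visit windows of 7 days either way, and 14 days for Visit 14 (Protocol section 4, 8.10, Appendix 1). A delay of up to 4 weeks may be carried forward (8.6). The rate window is 48 weeks from first dose (3.5.2; SAP 2.2.1).

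**Reproducing the plan's timeline.** Last dose = 4 × (12 − 1) = week 44. End of trial = 48 + 12 = week 60, as stated in the trial summary.

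**Formulas.** Let L be the week of the last dose, E the week of the final visit and W the week the rate window closes.
- Follow-up after last dose: F = E − L
- Part inside the rate: I = max(0, W − L)
- Share outside: (F − I) / F

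| Case | L | E | W | F | I | Share outside |
|---|---|---|---|---|---|---|
| On schedule | 44 | 60 | 48 | 16 | 4 | 12/16 = 75% |
| Last dose 1 week early | 43 | 60 | 48 | 17 | 5 | 12/17 = 71% |
| Last dose 1 week late | 45 | 60 | 48 | 15 | 3 | 12/15 = 80% |
| Visit 14 two weeks early | 44 | 58 | 48 | 14 | 4 | 10/14 = 71% |
| Visit 14 two weeks late | 44 | 62 | 48 | 18 | 4 | 14/18 = 78% |
| Full 4-week carried delay, calendar reading | 48 | 64 | 48 | 16 | 0 | 16/16 = 100% |
| Full 4-week carried delay, window closes at Visit 13 | 48 | 64 | 52 | 16 | 4 | 12/16 = 75% |

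The last two rows differ only in how '48 weeks' is read. If it is a fixed count of weeks from first dose, the window closes on the day of the delayed twelfth dose. If it means the treatment period ending at Visit 13, the window moves with the delay to week 52.

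**Against all time since first dose.** The part left out is 12/60 = 20%; the rate covers 48/60 = 80%.

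**Against the 100-day period in 9.3.** For an on-schedule completer, 4 weeks = 28 days are inside, so 72 of 100 days (72%) are outside. That period applies to early stoppers, and for many of them it would be the shorter limit. It fits wholly inside 48 weeks for anyone stopping by week 48 − 100/7 = 33.7. Someone stopping at week 12 would be cut off near week 12 + 14.3 = 26.3.

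**Person-time.** With 80 randomised and 10% drop-out, 72 remain, or 36 per arm. Weeks 48 to 60 then hold 36 × 12/52 = 8.3 person-years per arm, out of 36 × 60/52 = 41.5. The documents give no SAE rate. At an assumed 0.3 to 1.0 per person-year, that is about 2.5 to 8.3 SAEs per arm. This is an illustration only; nothing below depends on it.

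**The case against.** **A 48-week rate is a legitimate choice.** It matches the treatment period and the primary outcome. Protocol 8.10 allows COPD medication to change after week 48, and under COVID-19 restrictions Visit 14 was by telephone, without vital signs, examination or laboratory tests. Leaving out 12 weeks removes events and person-time together, so the 48-week rate is not biased for what it measures. All of this stands, and it is why the 48-week rate should be kept.

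**A reader might infer that late events are lost.** The documents do not support that. SAEs are reported to the final visit, Protocol 10.3 plans AE tables by arm with no 48-week limit, and SAP section 7 and Appendix 2 list all events with arm. Nor does SAP section 7 by itself contradict the outcome: it states what is recorded, and recording may properly be wider than an endpoint.

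**A reader might infer that delayed participants always lose all follow-up after the last dose.** That requires the full 4-week delay, carried forward, and the calendar reading of '48 weeks'. No frequency of delay is given, and a participant may instead miss the dose with no shift in schedule. SAP 2.1.1 ends study time at the Visit 13 date, though only for the primary outcome, so the other reading is open.

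**Timing of reactions.** Section 9.2.1 says systemic effects usually appear within hours of a dose, with later onset possible, and puts injection-site reactions mostly at one to two days. Four weeks covers those typical times. It does not settle the matter for infection, cardiovascular events or anti-drug antibodies.

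**Conclusion.** The point holds as a gap in the between-arm rate, not in data capture. For an on-schedule completer 75% of follow-up after the last dose lies outside the AE and SAE rate outcomes, or 71% to 80% across the permitted visit windows. The figure reaches 100% only with a full carried delay and the calendar reading. The loss is smaller for participants who stop treatment early, because more of their time off drug falls inside 48 weeks.

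Two wording faults stand whichever window is preferred. The all-visits heading in SAP 2.2.1 contradicts its 48-week bullets. 'Treatment-emergent' in Table 7 has no end date; Table 8 does not use the term, but its totals state no window either. In addition, neither table supplies a denominator for an event rate.

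The percentages rest only on the documents' schedule. Safety is summarised descriptively, so no test, power or sample-size figure changes. This is a cheap improvement to how a key objective is reported.

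**What to change.** 1. Report AE and SAE rates by arm from first dose to each participant's last safety contact (the final visit, nominally week 60, or withdrawal from the study), with actual person-time as the denominator.
2. Do not truncate at 100 days for those who stop treatment but stay in follow-up, as Protocol 7.10 and 8.7 intend. Such a cut would shorten the present window for anyone stopping before about week 34.
3. Keep the 48-week rate beside it, and state that it runs to Visit 13, which settles how carried delays are handled.
4. Reconcile the heading of SAP 2.2.1 with its bullets, and align Protocol 3.5.2.
5. State the same end date for 'treatment-emergent' in SAP Table 7 and for the totals in Table 8.
6. Declare the addition post hoc. The revision history places the version 2.1 changes after database lock and version 3.0 after that; SAP section 1 and 6.2 already provide for identifying such analyses.

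The cost is one table column and some wording, with no new data. The drawback is that weeks off drug, and COPD medication changes allowed after week 48, may slightly dilute the longer rate. Showing both windows lets the reader see this.
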